# Reporting of Unanticipated Problems, Adverse Events or Deviations

Any unanticipated problems, serious and unexpected adverse events, deviations or protocol changes will be promptly reported by the principal investigator or designated member of the research team to the IRB and sponsor or appropriate government agency if appropriate.

All participants will be evaluated for adverse events (AEs) during each study visit. All AEs will be recorded on an adverse event case report form. Based on the nature of the AE, study physicians will determine the severity of the event and the association with the study. All SAEs will be recorded on an IRB "Serious Adverse Event" case report form. SAE are defined as events that are (1) life-threatening or fatal; (2) result in severe or permanent disability; or (3) require hospitalization, other than brief emergent care for non-life threatening conditions. All SAEs will be reported to the IRB within seven calendar days of the investigator or other members of the study team becoming aware of the event. SAEs will be followed until resolution, even if study participation has been terminated.

The "severity" of events will be graded according to the following guidelines:

- 1. *Mild:* The patient is aware of, but can easily tolerate, the event;
- **2.** *Moderate:* The discomfort of the event is severe enough to interfere with some usual activities:
- 3. Severe: The patient is incapacitated, and unable to perform most or all usual activities.

The "study relatedness" will be assigned according to the following guidelines:

- 1. **Definitely Related:** The reaction follows a reasonable temporal sequence and is known to be an effect of the medication or procedure;
- **2. Probably Related:** The reaction follows a reasonable temporal sequence with reasonable suspicion that the study medication or procedure caused or contributed to the event;
- **3. Possibly Related:** The reaction follows a reasonable temporal sequence, and current medical knowledge does not preclude a relationship between the medication or procedure and the event:
- **4. Unlikely:** Current medical knowledge precludes a causal relationship between the medication or procedure and the event;
- **5. Definitely Unrelated:** The cause of the reaction is known to be other than the medication or procedure.

The following adverse events would preclude further participation in this study: (1) fasting plasma glucose >165 mg/dl on two consecutive visits; (2) evidence of symptomatic hypoglycemia, on two occasions following appropriate dietary and physical activity counseling; (3) clinically significant changes in neurological or medical status, including, but not limited to, stroke, myocardial infarction, new onset of kidney or liver disease, etc. The study physician will review all medical records to determine whether changes in medical status are significant and warrant removal from study participation.

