## **Objectives:**

- 1. Assess the safety and feasibility of a 4-month MMKD vs. the AHAD in adults with aMCI, and determine its effects on a key AD biomarker (CSF Aβ42 primary outcome), as well as on: cognition, cerebral metabolic rate of glucose utilization (CMRg) measured with F-FDG PET; brain ketone utilization assessed with C-acetoacetate PET; MRI measures of perfusion, hippocampal volume, default mode connectivity, and white matter integrity; and other CSF biomarkers (total tau, p-tau181).
- 2. Investigate response moderators: APOE genotype, amyloid PET positivity and metabolic status.
- 3. Investigate proposed mechanisms underlying MMKD effects, including: 1) neuronal activity and synaptic function (MRI, PET); 2) bioenergetic pathways (mitochondrial function assays, plasma neural-derived exosome markers); 3) epigenetic analyses; 4) CSF/blood multi-omic panels (proteomics, metabolomics, lipidomics, transcriptomics).

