## **DIET INTERVENTION**

#### Interventions and Interactions

All potential participants for the study will first undergo a screening visit. Upon enrollment participants will have a total of three Core study assessments (data may be collected over several days for each Core assessment as long as visits are completed within two weeks – imaging, LP, etc.) occurring at baseline, 8 and 17 weeks (on-diet assessments), and 24 weeks (post-diet follow-up assessment). In addition to Core study visits participants will have weekly diet education visits for the first eight weeks, then return at 12 weeks to assess diet compliance over the course of the diet intervention. On week's 9-11 and 13-16 participants will have weekly telephone contact with the study dietitian to discuss food selection, meal preparation and any issues with diet compliance.

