**Mid-Diet Study Visit:** The Mid-Diet visit occurs at week 8 (Visit 13) and will include diet education and compliance check, cognitive testing, stool and blood sample collection. At this visit additional measures will be recorded such as capillary glucose/ketone testing, weight and metabolic outcomes.

**Post-Diet Study Visits:** The Post-Diet Study Visits will occur during week 17 (Visits 15-17). At these visits, cognitive assessment, blood testing, capillary glucose/ketone testing, MRI, PET, DEXA, stool collection, and LP will occur.

**Post-Diet Follow-up Visit:** The Post-Diet Follow-up Visit will occur during week 24 (Visit 19) after participants have discontinued the diet and returned to an adlib diet. At this visit, cognitive assessment, blood testing, and capillary glucose/ketone testing will occur.

**Diet Educational Study Visits:** Over the course of the diet study, participants whether on the MMKD or AHA diet, will participate in a series of individual, group and phone educational visits to inform participants of diet specifics, develop personalized meal plans, ensure adherence to their diet, and answer any questions. The study dietician will lead these educational sessions in the clinic or by phone.

**In-Person Diet Education Sessions**: The Pre-Diet Education session will take place within 1 week prior to the start of the diet (90 min session). After diet initiation, for both diets, participants will meet with the study dietitian weekly for the firest 8 weeks of the study for continued diet education and assessment of compliance. Participants will return to the clinic at week 12 for diet education and compliance check.

If participant enrollment and scheduling permit group sessions, participants may meet as a group or individually during later weeks. These sessions will last from 30 min (individual) to 60 min (group) each and will provide participants support and the opportunity to ask questions. Diet guidelines will be reviewed at each session. However, if necessary to improve diet adherence and understanding, individual sessions with the study dietitian may take place as needed during the remainder of the study. The need for these sessions can be determined by the study dietitian and/or by participant request.

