# **Study Visit Measures**

*Clinical/Physical Evaluation*: During eligibility screening, participants will receive standardized clinical cognitive evaluation (ADCC UDS3), a clinical interview and physical/neurological exam, clinical labs, and depression screening with the Geriatric Depression Scale (GDS). 

**Metabolic Outcomes:** Fasting plasma or serum will be sent out for assay by LabCorp diagnostic company for glucose, insulin, and lipids (total cholesterol, LDL, VLDL, HDL, triglycerides) at screening, baseline, month 2, and month 4. Quick analysis of metabolic outcomes done in week 1 and 12 or to ensure participant safety may be delivered to the Wake Forest CLIA-certified laboratory for expedited processing. Capillary ketone levels and weight will be measured at each in-person visit in the center. Body composition will be measured using DXA at baseline and at the end of the diet intervention.

**Cognitive Testing Visits:** For all cognitive visits, participants will be asked to eat a standard meal the night before and fast for 12 hours prior to start of visit. Upon arrival, weight and vital signs will be obtained and then blood will be drawn (about 3 tablespoons). A breakfast meal will then be provided (standard meal for baseline visit and study meal (MMKD or AHAD) for other visits) and the cognitive protocol will begin. All cognitive test administration will be audio-recorded.

**Cognitive Battery:** The cognitive protocol will consist of both computerized and paper-based assessments and will include all components of the memory composite as well as additional assessments. Cognitive testing will be audiotaped using a digital recorder for quality assurance and random checks will occur for quality control and to correct drift. Recordings will be erased once review has been completed. The total cognitive battery will take approximately 60-75 minutes to administer at both screening and Core Study Visits. Methods for cognitive assessments and other evaluations are described in this section.

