## STATISTICAL CONSIDERATIONS

## Statistical Analysis and Power

Statistical analyses will be overseen by [name], Wake Forest ADCC Data Core member, who has extensive experience in the analyses of clinical trials and in using results from Phase II studies to design efficient Phase III trials. We will examine change in our primary outcome CSF AB42, using analysis of covariance to compare mean levels at 4-months between intervention groups with adjustment for baseline level, age, and MMSE. Two-sided type 1 error for the primary outcome will be controlled at 0.05 and the primary analysis (intention to treat) will include all data on participants grouped according to intervention assignment, regardless of adherence. If residuals from this model are markedly skewed, we will perform supporting analyses after data transformation. Similar approaches will be used for other secondary outcomes of our primary aim (e.g. PET, MRI, CSF). Mixed effect models will be used for repeated measures (cognition). To examine whether any differences in these outcomes are moderated by APOE genotype, amyloid PET positivity, insulin resistance (secondary aims), or by gender, we will use tests of their interaction with intervention assignment. Additional aims involve examining how changes among outcomes differ between intervention groups and whether they track with markers of hypothesized mechanisms. We will explore the intercorrelations among changes using multivariate decomposition and assess whether these differ between intervention groups. We will also assess mediation, using models in Emsley et al. 2010^84 to identify potential underlying mechanisms.

**Power Analysis for Primary Endpoints:** Sample size estimates for the proposed study were based on the results of our small pilot study showing 6-week mean MMKD vs AHAD diet changes in CSF

Aβ42 of 89 vs 11 units (pooled SD of changes 102). With 2-sided type 1 error of 0.05, if attrition is as large as 15% (our observed pilot attrition was 10%), and allowing a 10% attenuation of effect related to possible non-adherence, enrolling 53 participants/group provides >90% power: thus, we target N=60/group. The proposed longer 4-month intervention and covariate adjustment may increase power to detect a true difference.

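### The adverse-event stopping rule ends study participation, not just the diet, so a participant removed before the week-17 lumbar puncture has no 4-month CSF Aβ42

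*Combined protocol and SAP*

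**What the plan says.** The stopping rule stands in the protocol under Assessment of Safety, Reporting of Unanticipated Problems, Adverse Events or Deviations: "The following adverse events would preclude further participation in this study: (1) fasting plasma glucose >165 mg/dl on two consecutive visits". The second trigger is symptomatic hypoglycemia on two occasions after counseling. The third is a clinically significant change in neurological or medical status, where the study physician reviews records to "determine whether changes in medical status are significant and warrant removal from study participation". The same section says that serious adverse events are followed to resolution after participation has ended. It provides for no other follow-up.

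Table 2 (Schedule of Study Visits and Procedures) marks the LP at Visit 3 (baseline) and Visit 16 (week 17) only. The week-8 and week-24 visits have none.

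Statistical Analysis and Power compares 4-month CSF Aβ42 by analysis of covariance. The primary analysis, labelled intention to treat, "will include all data on participants grouped according to intervention assignment, regardless of adherence". No method is named for a missing 4-month value.

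The first objective begins: "Assess the safety and feasibility of a 4-month MMKD vs. the AHAD in adults with aMCI".

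**The concern.** Stopping an intervention and leaving a trial are separate decisions. Here one rule makes both. Because CSF is collected only once after baseline, removal at any time before Visit 16 costs the whole primary outcome for that participant. An analysis by assignment has then nothing to include. The loss follows a post-randomization event and may differ by arm. Lower glucose is expected on the ketogenic diet (Potential Risks and Protections Against Risks), which makes the hypoglycemia trigger more plausible there. The AHAD is 55-65% carbohydrate (Experimental Diet), which makes the high-glucose trigger more plausible there. The direction of any bias is therefore unknown.

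Safety data are affected too. Adverse events are collected at study visits, so routine collection ends for the very people who had a qualifying event, although safety is part of the first objective.

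**Working it through.** **Structure.** Three statements, side by side:
- the listed events end participation;
- after termination only serious adverse events are followed;
- the only post-baseline LP is at Visit 16.

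Together they mean that removal before Visit 16 leaves no 4-month Aβ42, and removal after it costs no primary outcome. No section describes an early-termination LP or an off-diet outcome visit. Week-8 cognition from a removed participant could still enter the mixed models, so the total loss concerns the primary outcome.

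**Timing.** Table 2 places on-diet metabolic blood draws before the LP at Visits 9, 13, 14 and 15, so removal can come late in the diet period. Visit 15 immediately precedes the LP visit. Under Interventions and Interactions, "data may be collected over several days for each Core assessment as long as visits are completed within two weeks", so a Visit 15 result could be back before Visit 16. The LP would then be cancelled after essentially full exposure. Whether this happens depends on laboratory turnaround, which is not given.

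**The plan's own sample size.** Inputs from Power Analysis for Primary Endpoints: changes of 89 and 11, SD 102, 10% attenuation, 15% attrition, two-sided 0.05.
- Difference: 0.9 × (89 − 11) = 70.2.
- Evaluable per group for 90% power: 2 × [(1.960 + 1.282) × 102 / 70.2]² = 44.4, rounded up to 45.
- Enrolled: 45 / 0.85 = 52.9, so 53. The stated figure reproduces (90.4% by the normal approximation, 89.8% by noncentral t).
- At the target of 60 per group with 15% missing, 51 are evaluable and power is 93.1% (noncentral t).

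**Shift in the treatment difference.** No removal rate is given, so I assume k = 1, 2 or 3 of 60 removed before Visit 16 and otherwise like the rest of their arm. If each would have lost L units of change by week 17, the retained data differ from the full assigned group by k × L / 60. The unadjusted standard error (SE) at 51 per arm is 102 × √(2/51) = 20.2.

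| Assumption | L | k = 1, 2, 3 (units) | At k = 3, in SE |
|---|---|---|---|
| MMKD only, back to zero change | 89 | +1.5, +3.0, +4.45 | 0.22 |
| MMKD only, falls to AHAD mean | 78 | +1.3, +2.6, +3.9 | 0.19 |
| Both arms, back to zero change | 89 − 11 = 78 net | +1.3, +2.6, +3.9 | 0.19 |
| MMKD only, off diet from week 8, loss proportional to time off | 78 × 9/17 = 41.3 | +0.7, +1.4, +2.1 | 0.10 |
| MMKD only, off diet from week 12, same | 78 × 5/17 = 22.9 | +0.4, +0.8, +1.1 | 0.06 |
| AHAD only, back to zero change | 11 | −0.2, −0.4, −0.55 | 0.03 |

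The range is about −0.6 to +4.5 units. Under proportional loss, removal at Visit 15 gives zero shift: it is lost data, not bias.

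**Power if removals come on top of 15% attrition** (difference 70.2): 92.3% at 48 vs 51 and 91.6% at 48 vs 48.

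**The case against.** The strongest reply is that hardly anyone will be affected. Inclusion criterion 8 requires normal fasting glucose, and exclusion criterion 5 removes people on diabetes medication. The protocol calls symptomatic hypoglycemia rare on the MMKD, and the second trigger needs two episodes after counseling. The third trigger is at the physician's judgement, and its examples, such as stroke, may rule out a research LP anyway. Poor compliance does not trigger removal; Diet Implementation and Monitoring answers it with more visits. All of this stands. It limits the size of the problem, but it does not supply the missing outcome.

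A second reply is that an LP taken weeks off diet answers a different question from an on-diet biomarker effect in a Phase II trial. That is a legitimate choice, but the analysis section states the opposite one. The protocol already accepts an off-diet assessment: the follow-up visit "will occur during week 24 (Visit 19) after participants have discontinued the diet and returned to an adlib diet".

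Third, the calculation treats removed participants as otherwise like their arm. It therefore measures the effect of stopping the diet, not selection by prognosis, and the 1 to 3 removals are assumed. That also stands. The 15% attrition allowance protects power but does not address losses that differ by arm.

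Some stronger readings do not hold. A reader might infer from Table 2 that a second high glucose reading could occur only at a few fixed visits. The documents do not secure this. Blood Collection Procedures/Measures lists fasting blood at Visits 6-13, for neuroendocrine measures, and Metabolic Outcomes allows extra analyses for participant safety. A reader might also infer that the intention-to-treat sentence promises collection after removal. It does not; it says only how available data are grouped.

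**Conclusion.** The point holds as a minor one. As written, the rule creates avoidable missing primary outcomes among participants removed before Visit 16 who could still safely have the LP, and this is at odds with the stated intention-to-treat analysis. The number is not given and is probably very small. With 1 to 3 removals per arm of 60, the shift is at most about 0.22 SE and power stays above 90%. These figures rest on the pilot means and SD, the assumed removal counts and the assumed change after stopping.

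A reader might conclude that the primary result is at risk. Nothing in the documents supports that. The consent form was not available and may contain follow-up wording. The reason to act is that the gap can be closed cheaply.

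**What to change.** In Reporting of Unanticipated Problems, Adverse Events or Deviations, change the consequence of the listed events, both in the opening clause and in the closing sentence on physician review, to discontinuation of the assigned diet. Leave the clinical criteria as they are. Then add:

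*Participants who stop the diet stay on their original schedule for the week-17 LP, cognitive and blood outcomes, the week-24 visit and adverse-event collection, where consent and the study physician's judgement allow. PET, MRI and DEXA are optional for them. The date and reason for stopping are recorded. Participation ends only if consent is withdrawn or the study physician judges study procedures unsafe.*

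This is a short amendment to protocol and consent that uses visits already scheduled. Its cost is a few off-diet visits for people who had a safety event, including an LP with its headache risk, plus radiation if the optional PET is done. The treatment difference would also be slightly smaller. With 3 of 60 MMKD participants retained at no treatment effect, the planning difference becomes 70.2 × 0.95 = 66.7, and power at 51 per arm is 90.5% instead of 93.1%. A sponsor that wants only an on-diet estimate can decline the off-diet LP, but should then say so in Statistical Analysis and Power.

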## ETHICS/PROTECTION OF HUMAN SUBJECTS

## **Informed Consent**

Signed informed consent will be obtained from each participant. Once participants have been identified for potential inclusion into the study, a study team member will explain the nature of the study and the study procedures by reviewing the material presented on the consent form. Potential participants who express interest in the study will then be asked to meet with the study coordinator in person, at which time the consent form will be reviewed again, and questions and concerns related to the study will be solicited. Once informed consent has been obtained, potential participants will undergo clinical evaluation to ensure they meet the inclusionary criteria for the study. To avoid coercion, the study team will stress, both in the initial telephone contact and in follow-up appointments: 1) that all research participation is voluntary, 2) that participants may withdraw at any time, 3) the decision to participate or not participate will not affect the participants' medical care or any benefits to which the participant is entitled, and 4) encourage questions about the study.

[name], the study coordinator, and project collaborators will develop the consent forms. The consent form will include all of the required elements of informed consent required by the FDA. The principles of informed consent in the current edition of the Declaration of Helsinki will be implemented.

Information will be given in both oral and written form. Participants, their relatives, guardians, or authorized representatives and informants will be given ample opportunity to inquire about the details of the study. All investigators will attend a training meeting prior to the start of participant recruitment. Informed consent will be documented by the use of a written consent form approved by the IRB and signed by the participant and/or a legally authorized representative.

Potential participants for this trial may be recruited from other ongoing studies in affiliation with the ADCC; data from blood, CSF, cognitive testing, and imaging measures may be utilized for this trial as long as a participant is enrolled within 6 months of the start of the diet intervention.

## Confidentiality and Privacy

Confidentiality will be protected by collecting only information needed to assess study outcomes, minimizing to the fullest extent possible the collection of any information that could directly identify participants, and maintaining all study information in a secure manner. To help ensure participant privacy and confidentiality, only a unique study identifier will appear on the data collection form. Any collected patient identifying information corresponding to the unique study identifier will be maintained on a linkage file, stored separately from the data. The linkage file will be kept secure, with access limited to designated study personnel. Following data collection participant identifying information will be destroyed within three years of study completion, producing an anonymous analytical data set. Paper documents will be placed in Cintas bins and electronic data will be deleted. Data access will be limited to study staff and personnel from collaborators that will help with data analysis. Data and records will be kept locked and secured, with any computer data password protected. No reference to any individual participant will appear in reports, presentations, or publications that may arise from the study.

